Objective 3. (Secondary) Effect of CBT on Cognitive Outcomes. We hypothesize that the CBT-OSA group will have better cognitive outcomes than the Education group over time. ANOVA will be applied to the California Verbal Learning Test, Delayed Free Recall Score with the primary endpoint at Day 365.

Objective 4. (Secondary) Effect of CBT on PTSD. We hypothesize that the CBT-OSA group will have fewer PTSD symptoms than the Education group over time. ANOVA will be used to

test group differences over time in the total score on the PTSD Checklist for DSM-5 (PCL-5), measured at Days 0, 21, 365. Primary endpoint is Day 365.

Table 1: Description of Measures

Table 1. Description	
Primary Outcome Measure:	
Hypothesis 1 Effect of CBT on CPAP adherence	
Objectively Measured CPAP Usage. The times when	The primary outcome measure is an objective
the mask is on the face are recorded and stored by the	measure: the average of CPAP mask-on time for
CPAP device ResScan™ data card.	the last 30 days of the 1-year RCT (Days 335-365).
Secondary Outcome Measures:	,
Hypothesis 2 Effect of CBT on Self-reported	
Everyday Activities, Mood and Quality of Life	
The Functional Outcomes of Sleep Questionnaire (FOSQ) [12] is a self-report measure of how much sleepiness impacts everyday activities and quality of life in multiple domains of function.	The FOSQ is designed to be given to individuals with a sleep disorder. In a 2011 VA clinical trial, FOSQ scores improved significantly in Veterans randomly allocated to APAP (n=105) and those allocated to CPAP (n=96), p's < .0001.
Hypothesis 3. Effect of CBT on Cognitive Outcomes.	
A cognitive battery known to be sensitive to OSA, and relevant to long-term CPAP adherence [9] will include our primary outcome measure, the California Verbal Learning Test [13], Long Delay Free Recall.	The purpose of the battery is to assess if changes in cognitive function occur, dependent on intervention group status. Baseline scores will also be used in supplementary data analyses on Moderators of treatment response to identify characteristics of patients who are best served by a CBT approach.
Hypothesis 4. Effect of CBT on PTSD.	
PTSD Checklist for DSM-5 (PCL-5) [14]. PCL-5 is a	The PCL-5 is designed to assess if the proposed
20-item self-report measure for PTSD based on DSM-5.	treatment has any effects on PTSD symptoms.

RESEARCH DESIGN AND METHODS PROCEDURES INVOLVING ELIGIBLE PARTICIPANTS

Study Timeline Schedule of Visits and Key Assessments

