	Consent	Screen	BL*	Pre- Intervention Phase		Early Intervention Phase			Booster Session Phase			Final Booster Session
Treatment Session				1	Start CPAP	2	3	4	5	6	7	8
Procedure Day		-28 to	-14	0		7	14	21	90	180	270	365
Consent	Χ	Χ*										
Med Hx review		X	Χ*									X
Blood Sample				Χ								
Self-reports		Х	X*					Х	Х	Χ	Χ	Х
Semi-structured Clinical Interview		Х	Χ*									Х
Cognitive Battery		Х	X*									Х
Self-Efficacy Measure for Sleep Apnea				Х				Х	X	X	Х	Х
Working Alliance Inventory SAT**				Х		Х	Х	Х	X	Χ	Х	Х
In-clinic treatment sessions				Х		Х	Х	Х	X	X	Х	Х
CPAP Usage (Measurement Periods)					× _				-	>		

^{*}If Baseline (BL) visit is needed, it will include the activities that were not completed during the screening visit

After Session 1 (Day 0), participants will be called by their CP or ED daily for one week to provide early and consistent intervention.

^{**}WAI modified to apply to Sleep Apnea Treatment (SAT).

OVERVIEW

Aims and Design of the Study. To test the efficacy of CBT-OSA in improving CPAP usage, the design will be a 2-arm RCT: 120 PTSD Veterans who are recently diagnosed with OSA and newly initiating CPAP will be allocated by 1:1 random assignment to either the 'CBT-OSA' group or the Education group. All Veterans will participate in usual care in VAPAHCS Pulmonary Service which is considered standard of care. During the 1-year study, the CBT-OSA arm will include seven individual, in-clinic intervention sessions with a CBT-trained Clinical Psychologist (CP): one session prior to starting CPAP (Session 1-Day 0), followed by three in-clinic sessions within the first four weeks of initiating CPAP (Session 2-Day 7; Session 3-Day 14; Session 4-Day 21) and 3 booster sessions (Session 5-Day 90; Session 6-Day 180; Session 7-Day 365). Education participants will receive equivalent amounts of contact with a trained Educator. All participants will receive the same CPAP devices and appropriate follow-up as usual care at the VAPAHCS.

To test the efficacy of CBT-OSA, the two groups will be compared for differences in average hrs/day of CPAP use. We are particularly interested in the difference between the groups in CPAP usage during the final 3 months of this 1-year study. Group differences in average hrs/day of CPAP use during Weeks 0-4 will be examined as a secondary outcome.

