The results of all of the screening assessments will be reviewed with Key Personnel. After consensus determination for study eligibility, the Study Coordinator will contact the participant to schedule a Baseline visit (if eligible), or provide appropriate referral and explanation (if deemed ineligible).

Enrollment, Randomization, and Baseline Measures

RCT Enrollment and Randomization. After the two-phase screening, eligible participants will be invited to participate and, if willing, scheduled to begin within 3 to 4 weeks of the completion of the screening visit. The Baseline visit and Session 1 (Day 0) will be carefully coordinated with Pulmonary staff for the participants who will receive their CPAP on the day of Session 1 (before the start of Session 1). All eligible participants will be randomized by the Data Manager to one of the two intervention arms: "CBT-OSA" or "Education" and notify the treating CP or ED, respectively.

Baseline Measures. The Coordinator will administer a cognitive battery

Adherence Intervention: CBT-OSA vs. Education

All CBT-OSA treatment will be done by a CBT-trained Clinical Psychologist and aimed at changing a participant's behaviors and cognitions related to CPAP use. These cognitive and behavioral interventions will be taught in the initial four weekly clinic sessions and reinforced in three booster sessions. To increase motivation and positive expectations, CBT-OSA will also include treatment goals relevant to the particular participant's condition.

The treating CP will work closely with the PI for clinical supervision and protocol adherence. The CP will learn the CBT-OSA intervention and will be practiced in achieving treatment fidelity. The CP will work with the participant individually (during certain sessions with the participant and bed partner).

The Education arm will focus on educational material (e.g., sleep health, sleep disorders, PTSD, cardiovascular health) over four weekly sessions and reinforced in three booster sessions. All participants will have equal opportunities for contact time with research staff. Participants will bring their CPAP to all sessions to use for exposure intervention (if in CBT-OSA) and to allow study staff to download CPAP data.

Pre-CPAP Intervention Phase

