On Day 0, prior to starting or reinitiating CPAP (Pre-CPAP Intervention Phase), the Veteran will complete the following self-report measures: FOSQ, ESS, PCL-5, BDI-II, SEMSA and WAI-SAT. Then, participants in both arms, will have one individual in-clinic session (Session 1-Day 0) with their assigned CP or ED.

MEASURES

Consented Veterans who have been determined eligible and are willing to enter the RCT will be administered the measures described in Table 1 above.

DATA ANALYTIC PLAN

Hypothesis 1. (Primary Outcome) Effect of CBT on CPAP usage. We hypothesize that the CBT-OSA group will use CPAP more hours per night on average than the Education group. An ANCOVA will be used to compare performance on the primary measure [(the average of CPAP mask-on time for the last 30 days of the 1-year RCT (Days 335-365); a continuous variable)] by Group (CBT-OSA versus Education). The analyses will be an intention to treat design using multiple imputation for missing data [19]. We will perform multiple regression analyses to identify potential covariates (e.g., AHI prior to treatmen1, daytime sleepiness) which will be considered in the analysis. In a RCT, we assume that the groups will be apportioned relatively equally on relevant background variables, but we will verify this by analyzing specific baseline

variables (e.g., gender, age, education). We do not propose to enter all possible background variables as covariates into this analysis; however, we will perform multiple regression analyses to identify significant covariates. We will then include those variables in the ANOVA as covariates.

Hypothesis 2-4. (Secondary Outcomes) Effect of CBT on Self-reported Everyday Activities, Mood and Quality of Life, Cognitive Outcomes and PTSD. Secondary analyses will be conducted to compare performance between groups at Day 365 on relevant measures listed in Table 4 using the same statistical approach as Hypothesis 1.

Hypothesis 2. Effect of CBT on Self-reported Everyday Activities, Mood and Quality of Life. We hypothesize that after initiating CPAP treatment, Veterans in the CBT-OSA group will report more improvement in the ease of performing everyday activities compared to that reported by those in the Education group. An ANOVA will be used to compare performance on the FOSQ Total Score (continuous variable) by Group at Day 365.

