Cognitive Behavioral Therapy to

Increase CPAP Adherence in Veterans

with PTSD

Statistical Analysis Plan

NCT02641496

October 6, 2023

DATA ANALYTIC PLAN

Hypothesis 1. (Primary Outcome) Effect of CBT on CPAP usage. We hypothesize that the CBT-OSA group will use CPAP more hours per night on average than the Education group. An ANOVA will be used to compare performance on the primary measure (CPAP mask-on time, a continuous variable) by Group (CBT-OSA versus Education group) at the end of the 1-year RCT (Day 365) adjusting for baseline CPAP mask-on time values. The analyses will be an intention to treat design in which drop-outs after the baseline evaluation will not be replaced. Their last CPAP mask-on time score will be considered their final score. Potential covariates (e.g., AHI prior to treatment, daytime sleepiness) will be considered in the analysis. In a RCT, we assume that the groups will be apportioned relatively equally on relevant background variables such as age, but we will verify this by presenting descriptive statistics on such variables. We do not propose to enter all possible background variables as covariates into this analysis.

Hypothesis 2-4. (Secondary Outcomes) Effect of CBT on Self-reported Everyday Activities, Mood and Quality of Life, Cognitive Outcomes and PTSD. Secondary analyses will be conducted to compare performance between groups at Day 365 on relevant measures listed in Table 4 using the same statistical approach as Hypothesis 1.

Hypothesis 2. Effect of CBT on Self-reported Everyday Activities, Mood and Quality of Life. We hypothesize that after initiating CPAP treatment, Veterans in the CBT-OSA group will report more improvement in the ease of performing everyday activities compared to that reported by those in the Education group. An ANOVA will be used to compare performance on the FOSQ Total Score (continuous variable) by Group at Day 365. Potential covariates: sleep efficiency.

Hypothesis 3. Effect of CBT on Cognitive Outcomes. We hypothesize that the CBT-OSA group will have better cognitive outcomes than the Education group over time. An ANOVA will be used to compare performance on CVLT-II Delayed Recall Score (continuous variable) by Group at Day 365. Potential covariates: education.

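### No step is described to obtain stored CPAP usage from Veterans who miss the Day 365 session, so their primary endpoint may be imputed or carried forward although the actual record may be obtainable

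*Protocol*

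**What the plan says.** **Storage.** Protocol Table 1 says the times when "the mask is on the face are recorded and stored by the" "CPAP device ResScan™ data card". It gives no capacity or retention period and mentions no remote transmission.

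**Collection.** Protocol, *Adherence Intervention: CBT-OSA vs. Education*: the device is brought to every session, in CBT-OSA for exposure work and in both arms "to allow study staff to download CPAP data". The visit table has a CPAP usage row that begins when CPAP starts, but it names no collection method. Neither document mentions mailed cards, usual-care downloads, or continued collection after a participant stops attending.

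**Endpoint.** The protocol's Data Analytic Plan takes Days 335-365. The SAP places the comparison at Day 365.

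**Sessions.** The protocol Overview lists four early sessions (Days 0, 7, 14 and 21) and then "3 booster sessions (Session 5-Day 90; Session 6-Day 180; Session 7-Day 365"). The visit table shows eight sessions, including one at Day 270.

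**Missing values.** Protocol: "The analyses will be an intention to treat design using multiple imputation for missing data". SAP, Hypothesis 1: "Their last CPAP mask-on time score will be considered their final score".

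**The concern.** Attending sessions and using CPAP are different behaviours. A Veteran can stop coming to the clinic and go on using the device, which would continue to store mask-on times. Under the collection route as described, that person has no Days 335-365 value, and both documents then go straight to a substitution rule without first seeking the record.

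This matters more here than in most trials because the trial tests an intervention on adherence. Missingness in an objective primary outcome is tied to attendance, which may be related to CPAP use and may differ by arm. The protocol gives one reason why capture could differ: in CBT-OSA the device is brought for exposure work as well as for download, in Education only for download. That makes differential capture plausible but does not show it. Intention to treat is promised in both documents, and it has most substance when outcome data are sought on everyone randomised.

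The point concerns whether data are collected. How known stopping of CPAP should be scored is a separate question.

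**Working it through.** **1. Which session can capture the window.** The window opens on Day 335. Of the scheduled sessions, only Day 365 falls in or after it. If Day 365 is missed, the last possible earlier download precedes the window by:
- Day 270 (visit table): 335 − 270 = 65 days
- Day 180 (Overview text): 335 − 180 = 155 days
- Day 21 (attendance stops after the weekly phase): 335 − 21 = 314 days

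No earlier download holds any part of the endpoint.

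**2. Figures in the plan.** There is none to reproduce. The documents give 120 participants allocated 1:1, so 60 per arm. They state no alpha, power, effect size, SD or drop-out rate. Everything below is illustration under assumed inputs.

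**3. Bias in the group difference.** Let m be the share of an arm with no endpoint download, and g the substituted minus the true hours per night in those people, taken as equal in both arms.

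Bias = m(CBT-OSA) × g − m(Education) × g

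| Missing, CBT-OSA / Education | g (h/night) | Bias (h/night) |
|---|---|---|
| 15% / 30% | 1 | 0.15 − 0.30 = −0.15 |
| 15% / 30% | 2 | 0.30 − 0.60 = −0.30 |
| 10% / 30% | 2 | 0.20 − 0.60 = −0.40 |
| 20% / 20% | 1 to 3 | 0 |

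Over 10-30% missing, with Education losing 10-20 points more and g of 1-3 h, the bias runs from −0.1 to −0.6 h. A negative sign is against CBT-OSA. It reverses if CBT-OSA loses more, or if substituted values are too low.

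If the estimate rests on attenders, or on imputation from arm alone, g is the attender minus non-attender gap. Under carry-forward, g is each person's last downloaded value minus true final use. Under imputation that uses interim downloads, g should be smaller, but later changes in use remain unseen.

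**4. Precision.** Complete-case standard error relative to full data:
- 15% / 30% missing: √[(1/(60 × 0.85) + 1/(60 × 0.70)) / (2/60)] = √[(1/51 + 1/42) / (1/30)] = 1.141
- 20% in each arm: √(1/0.80) = 1.118

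These ratios do not apply to carry-forward, which removes nobody from the analysis.

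**5. What retrieval would do.** Take 15% / 30% missing, attenders at 4 h (an arbitrary level that cancels), half of the missing cards retrieved at random, and the rest filled with the arm's observed mean.
- Gap 1 h: CBT-OSA (0.85 × 4 + 0.075 × 3)/0.925 = 3.919; Education (0.70 × 4 + 0.15 × 3)/0.85 = 3.824. Estimated difference 0.095, true difference 3.85 − 3.70 = 0.15, bias −0.055 h.
- Gap 2 h: 3.838 − 3.647 = 0.191 against a true 0.30, bias −0.109 h.

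In this model, retrieving half the cards reduces the bias from 0.15-0.30 h to about 0.05-0.11 h.

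**The case against.** **Silence is not exclusion.** The protocol says why devices are brought to sessions. It does not say that this is the sole route, or that collection ends when attendance does. Participants remain in usual Pulmonary care, and screening materials give permission to review medical records. This stands: it is unsafe to claim that session download is the exclusive route. What remains is that no other route is described.

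**The record may not exist.** A reader might infer that every non-attender's Days 335-365 data sit on a card and are being discarded. The documents do not support that. Table 1 says mask-on times are stored but not for how long. The protocol lets Veterans decline CPAP, and a participant could also return or lose the device or withdraw consent. The data may be obtainable for some non-attenders, and no more can be said.

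**Day 365 is more than an intervention session.** It also carries the self-reports, clinical interview and cognitive battery, so missing it is not purely disengagement from CBT or education. If the card does retain the full year, missed earlier sessions cost no endpoint data, and nothing in the text bars a late download. The SAP also does not define a drop-out by missed sessions. All of this stands, and it narrows the exposure to one visit. It also makes the remedy easy, since one late download could recover the window.

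**The illustration models neither document's rule.** Correct. The SAP carries forward each person's own last value, and the protocol's imputation model is unspecified and could use interim downloads. The 15%/30% split is an assumption.

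**Conclusion.** The point holds as a gap in the collection plan. The one route described depends on attendance, only the Day 365 session can capture the endpoint, and both documents substitute a value without a step that first seeks the stored record. This is more than a missing operational detail, because following the plan as written can replace an objective primary outcome with an estimate when the measurement might have been had cheaply.

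Its size cannot be established from the documents. The 0.15-0.30 h/night against CBT-OSA rests on assumed 15%/30% missingness, an assumed 1-2 h gap, and analysis by complete cases or by imputation from arm alone. It would be smaller with imputation that uses interim downloads, and zero with equal missingness and gap. It is not a prediction for this trial. A change is advisable, with medium confidence, since retrieval may already be practised without being written down.

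**What to change.** **Protocol, *Adherence Intervention: CBT-OSA vs. Education*.** State that device data through Day 365 will be sought for every randomised participant regardless of session attendance, unless consent is withdrawn. If the Day 365 session is missed, obtain the card by prepaid mail, a late download or a usual-care Pulmonary visit, and compute the actual Days 335-365 mean from the stored dates.

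**SAP, Hypothesis 1.** State that the missing-data rule applies only when the record cannot be obtained. Reconcile that rule with the protocol: one document specifies multiple imputation and the other carries the last value forward, and the choice decides how every unretrieved case is analysed.

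**Schedule.** Reconcile the visit table (eight sessions, with Day 270) with the Overview text (seven, without it), since this determines the last interim download.

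**Cost.** Postage, a telephone call and some staff time for each non-attender, and a few results arriving after the Day 365 date. Two checks come first: that the consent wording covers retrieval after attendance stops, and that the card retains nightly data long enough for a late download to include the whole window.

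### Protocol and SAP give different primary analyses with no stated precedence, and the SAP's one fixed covariate, baseline mask-on time, has no scheduled measurement

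*Protocol*

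**What the plan says.** **Protocol (30 April 2024), Data Analytic Plan, Hypothesis 1.** The test is an ANCOVA by group on mean mask-on time over Days 335-365. AHI and daytime sleepiness are given as examples of covariates, and the rule for entry is: "we will perform multiple regression analyses to identify significant covariates. We will then include those variables in the ANOVA as covariates". There is no threshold and no closed list. On missing data: "The analyses will be an intention to treat design using multiple imputation for missing data". No baseline usage term is named.

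**SAP (6 October 2023), Hypothesis 1.** The test is an ANOVA by group at Day 365, with no averaging window, "adjusting for baseline CPAP mask-on time values". On other variables: "Potential covariates (e.g., AHI prior to treatment, daytime sleepiness) will be considered in the analysis". There is no significance screen. On drop-outs: "Their last CPAP mask-on time score will be considered their final score".

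**When usage can first be recorded.** In the protocol's Aims and Design of the Study, the participants are those "who are recently diagnosed with OSA and newly initiating CPAP will be allocated by 1:1 random assignment". The schedule row "CPAP Usage (Measurement Periods") begins in the column for the start of CPAP. RCT Enrollment and Randomization refers to participants who "will receive their CPAP on the day of Session 1 (before the start of Session 1"). The Pre-CPAP Intervention Phase text allows that some may be restarting CPAP.

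**Hypotheses 2-4.** Both documents refer back to the approach for Hypothesis 1. Neither names the baseline score of FOSQ, CVLT-II delayed recall or PCL-5 as a covariate.

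**The concern.** The trial has one primary test, and an analyst holding both documents cannot tell which model was pre-specified. They differ on covariates and on missing data, and the outcome window is explicit in only one of them.

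The SAP's baseline term matters most. It is that document's only mandatory covariate, yet no visit supplies it for someone new to CPAP. An analyst who needs a value may turn to the first days or weeks of use. Those data arise after allocation and after the arms have begun to diverge at Session 1. The protocol itself plans to compare the arms on usage in Weeks 0-4, so an early effect is something that the trial expects it might see. Adjusting for it would remove part of the effect under test.

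**Working it through.** **1. Side by side**

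| Element | Protocol | SAP |
|---|---|---|
| Outcome | Mean over Days 335-365 | Day 365, window not stated |
| Fixed covariate | None | Baseline mask-on time |
| Other covariates | Kept if significant; open list | Considered; open list |
| Missing data | Multiple imputation | Last score carried forward |
| Precedence | Not stated | Not stated |

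**2. Inputs.** From the documents: N = 120, allocated 1:1, so 60 per arm. The documents give no alpha, SD, effect size or power, so there is no stated figure to reproduce. Assumed: two-sided 5%, final effect 0.5 SD, correlation r between early and final usage of 0.6 (range 0.4-0.8), early effect 0.1, 0.25 or 0.5 SD.

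**3. Baseline term set to zero for all.** The columns are intercept, group and a constant zero. The design matrix has rank 2 with 3 columns, so the term cannot be estimated and drops out. The group comparison is the unadjusted one: SE = sqrt(2/60) = 0.183 SD, noncentrality 0.5/0.183 = 2.74, power 77.5%.

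**4. Baseline term filled with early on-treatment usage.** Expected estimate = final effect - r × early effect. At r = 0.6:

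- early effect 0.1: 0.5 - 0.06 = 0.44 SD
- early effect 0.25: 0.5 - 0.15 = 0.35 SD
- early effect 0.5: 0.5 - 0.30 = 0.20 SD

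Approximate SE = sqrt((1 - 0.36) × 2/60) = 0.146 SD. It is slightly larger in practice because the arms differ on the covariate. The noncentralities are about 3.0, 2.4 and 1.4. Simulated power (20,000 trials per cell) is about 85, 65 and 25%.

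If the final effect is zero, the expected estimates are -0.06, -0.15 and -0.30 SD. The test then rejects in about 6-7, 17 and 50% of trials, mostly against CBT-OSA.

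Matched cells across the correlation range, final effect 0.5 SD:

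| r | Early effect | Estimate | Power |
|---|---|---|---|
| 0.4 | 0.25 | 0.40 | about 65% |
| 0.8 | 0.25 | 0.30 | about 76% |
| 0.8 | 0.5 | 0.10 | about 14% |

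**5. The protocol's screen, applied mechanically.** This was simulated with 2 candidates (AHI, sleepiness) or 5 (adding gender, age and education). Type I error is 4.8-5.7%, against 4.9-5.3% for a fixed two-covariate model, and never more than 0.4 points apart in the same setting. Four reasonable readings of the rule (threshold .05 or .10, group in or out of the screening regression) pick different covariate sets in 11-17% of trials with 2 candidates and 26-37% with 5. The rule is open, but it does not itself inflate error materially.

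**6. Hypotheses 2-4.** At an assumed 0.5 SD effect, adjusting for the outcome's baseline score raises power from 77.5% to 88, 92 or 97% at r = 0.5, 0.6 or 0.7. This is the distance between two readings of the text, not a demonstrated loss.

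**The case against.** **The SAP does not say to use early usage.** This is correct. The most literal reading for new starters is zero, which does no harm. The bias in step 4 is what follows if the gap is filled in one tempting way. Nor does every such filling cost power: with an early effect of 0.1 SD and r = 0.6, power rises to about 85%, although the estimate still shrinks to 0.44 SD.

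**A reader might infer that the analysis would be cut down to participants with earlier CPAP data.** The SAP states no such restriction, and the documents give no share of restarters. The sentence on receiving the device on the day of Session 1 can also be read as covering only some participants. Earlier values may therefore exist for a few, but nothing schedules them for the rest.

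**A reader might infer that the significance screen inflates type I error.** Step 5 does not support that. Choosing the most favourable subset after seeing results would give up to 5.9-8.0% (2 candidates) or 7.0-9.8% (5), but the protocol does not prescribe that. Replacing the screen with a fixed list is partly preference.

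**The endpoints may not conflict.** Day 365 at the end of the trial is compatible with a mean over Days 335-365. What stands is that the SAP leaves the window unstated, while the protocol's overview also stresses the final 3 months.

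**Hypotheses 2-4 may already be baseline-adjusted.** Under the SAP this is a fair reading, since its Hypothesis 1 approach adjusts for baseline. The protocol's approach has no such term.

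**A reader might take the later protocol to supersede the SAP.** Neither document says so.

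**Conclusion.** The point holds. The two documents specify different covariate rules and different missing-data methods for the primary test, with no stated precedence, and the SAP's only fixed covariate has no scheduled measurement in people newly starting CPAP.

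The size depends on how the missing baseline is filled. Zero for all costs nothing. Early on-treatment usage biases the estimate by minus r × early effect: at r = 0.6, from 0.5 SD to between 0.44 and 0.20 SD, with power between about 85 and 25%. These figures rest on assumed effects and correlations, because the documents give none. They show what the wording permits, not what the sponsor intends. The effects of the endpoint wording and of the choice between imputation and last score carried forward were not quantified; on those the finding is textual.

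**What to change.** 1. Delete the SAP's baseline mask-on term, and bar any usage recorded after randomisation as a covariate in the primary model.
2. State one identical primary model in both documents: mean mask-on hours over Days 335-365 (as in the protocol's Objectives, Table 1 and Data Analytic Plan) on group, with multiple imputation in place of the last score carried forward, and a closed covariate rule. Either of two rules would do:
   - a short fixed list of pre-randomisation variables, such as pre-treatment AHI and a sleepiness score recorded before allocation; or
   - a closed candidate list with a stated threshold and a rule for selecting across imputed data sets.

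   The protocol gives no day for randomisation, so a Day 0 Epworth score should be used only if it is completed before the arm is disclosed. The Epworth scale mailed before the sleep study is a possible alternative source.
3. For Hypotheses 2-4, say in both documents that each outcome's own baseline score (FOSQ, CVLT-II delayed free recall, PCL-5), recorded before the arm is disclosed, is a covariate. All three are already collected.
4. State which document governs.

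The cost is wording and a few degrees of freedom, with no new data. A fixed AHI-plus-sleepiness list loses about 1 point of power or less against selection if no candidate is prognostic. It loses about 6-7 points (77% against 83-84%) if those two are uninformative while two other named variables are prognostic (assumed coefficient 0.3). The documents do not show which case applies, which is why a closed selection rule is also acceptable.
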